To avoid alerting subjects to the fact that we are directly studying the effect of the patient-provider relationship on health outcomes (which could influence study results^{69,70}), subjects will be told during the consent process that 1) we are studying the relationship between their symptoms, their physiology, and their response to amitriptyline or omeprazole and 2) we are studying whether physicians mirror patients' physiology as has been suggested by some neuroimaging studies^{40,71} (to explain why providers are being similarly monitored). While it is challenging to study patient-provider interactions without subjects' direct knowledge, particularly since both are being monitored in this study, we believe that framing the study in this way is the most sensible way to proceed and the least likely to substantively affect the study's results. As the standard vs. expanded visit intervention is minimal risk, we believe it meets the federal criteria for modification of informed consent⁷², which allows us to conceal from participants that we are studying the patient-provider interaction.

Individuals who sign the informed consent document and elect to participate in the study will be considered enrolled. Only individuals who can provide informed consent will be eligible to participate.

Provider Recruitment and Screening:

We will advertise the study to primary care internal medicine and family medicine physicians and nurse practitioners via email. We may also recruit providers from the division of gastroenterology. We may also present the study at practice group meetings. Providers must be willing to adhere to the study protocol and not provide specific treatment recommendations (pharmacologic or non-pharmacologic) as this is outside the scope of the study. Providers must also be willing to receive a brief training to understand how to deliver the standard and expanded visit interventions.

Provider Consent:

Participating providers will be consented by the study PI. As study providers will deliver both visit interventions, they will be trained in both visit type formats. Providers will be notified of which intervention they are delivering immediately before walking into the room to conduct the study visit.

Randomization:

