5. STUDY INTERVENTIONS

5.1 Interventions, Administration, and Duration

Subjects will be randomized to receive either a “standard visit” or an “expanded visit” with a study provider. The standard visit is based on a high quality, empathic, conventional primary care encounter. The expanded visit is based on an integrative medicine consultation. Both visits are based on a script of questions and statements to the patient/subject (see Appendix E). The standard visit script includes questions about GERD history, symptoms, prior evaluation and treatments, and past medical history as well as a brief physical exam. The expanded visit script includes the same questions as the standard visit script plus additional questions that inquire about the modalities of their GI symptoms (e.g., nature of the reflux taste, sensation of heartburn pain and/or abdominal fullness, time of day better/worse), details about non-GI symptoms, quality of sleep, the effect of the weather on symptoms, food cravings and aversions, menstrual flow, fears/phobias, and overall temperament. In this way, the expanded visit tries to understand the patient’s/subject’s constitution in a way that many systems of integrative medicine attempt to do. To reduce the potential for introducing bias by using the words “standard” and “expanded”, the visit templates that the study providers will follow will simply refer to the number of questions to be asked on the template (e.g., 6 Question Template).

At the end of both the standard and expanded visits, the provider will recommend the subject take the study medication and describe how to take it and what to expect. Subjects will receive the same scripted advice in both groups. Each subject will receive an 8-week supply of amitriptyline or omeprazole with instructions for how to take it (10 mg daily at bedtime or 20 mg daily when waking up, respectively).

In our pilot study⁶⁴ we did not limit the amount of time spent with the study subject. On average, the standard visit lasted 18 minutes (range 11-32 minutes) and the expanded visit lasted 42 minutes (range 23-74 minutes). The study providers will be instructed to maintain equal empathy in both groups (e.g., kind and friendly manner, maintain eye contact, active listening and repeating back the patient’s words, expressions of empathy). Thus, the main differences between the visits will be the length of time spent with the subject and the additional questions that are asked.

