- Baseline Symptom Diary – 7-day diary indicating the frequency and severity of 9 different GERD and dyspepsia-related symptoms on a 5-point scale as well as any medications, supplements, or other products used to help manage symptoms. The first 3 symptoms (daytime heartburn, nighttime heartburn, and acid reflux) will be used to assess severity of GERD symptoms.
- GERD-HRQL – a validated 11 item scale for assessing the impact of GERD symptoms on health-related quality of life⁷³.
- NIH PROMIS GERD scale – a validated 13 item instrument assessing frequency and severity of GERD symptoms over a 7-day recall period²⁶.
- GSRS: The Gastrointestinal Symptom Rating Scale is a validated 15 item instrument for measuring the severity of gastrointestinal symptoms⁷⁴. It contains 5 subscales: abdominal pain, reflux syndrome, diarrhea syndrome, indigestion syndrome, and constipation syndrome.
- Current Stress Question – 1 item self-report measure of current stress level on a scale of 0 (no stress) to 10 (extreme stress)
- Perceived Stress Scale (PSS) – a widely used 10 item measure of perceived stress that has been shown to correlate with a variety of different health outcomes⁷⁵. We have adapted the originally validated measure to ask about stress over the past week (7 days), rather than the past month, to better fit the timeframe of the study. We have used this timeframe in other studies.
- NEO Five Factor Inventory (NEO-FFI) – a validated 60 item instrument that measured five major dimensions of personality: extraversion, neuroticism, agreeableness, conscientiousness, and openness to experience⁷⁶. Some dimensions have been associated with response to enhanced patient-provider interactions in others' studies⁷⁷.
- Physiologic Measures and Video Recording: During the intervention we will measure HRV, respiratory rate, skin temperature, and GSR in both study patients and study providers. The study visit will also be video recorded. During the COVID-19 pandemic, in order to allow us to collect physiologic and nonverbal behavior data (e.g., smiles) with the patient and physician unmasked, while also complying with institutional and state public health guidelines, the patient and doctor will sit in separate but adjacent, exam rooms with the door closed and use a video telehealth platform (e.g., Zoom, Cisco Meeting) to communicate. We will use the recording function to capture video data.

Evaluations for study providers:

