9. STATISTICAL CONSIDERATIONS

9.1 General Design Issues

Design: This is a single-blinded randomized controlled trial in which subjects will be randomized in a 1:1 fashion to receive either an expanded or standard visit with a healthcare provider about their GERD symptoms and then treated with amitriptyline or omeprazole for 8 weeks to determine whether an expanded visit can augment the effects of a medication compared to a standard visit.

Primary hypotheses:

1. Subjects who receive an expanded visit will have a greater improvement in their GERD symptoms after 8 weeks of treatment with amitriptyline or omeprazole compared to subjects who receive a standard visit.

Secondary hypothesis:

1. Patient-provider dyads in expanded visits will have a greater percentage of the total visit time spent in physiologic concordance (measured by either GSR or HRV) compared patient-provider dyads in standard visits.
2. Percentage of visit time with physiologic concordance (in GSR or HRV) will be correlated with GERD symptom improvement.
3. Subjects who experience physiologic changes similar to those elicited by mind-body techniques (i.e., decreased GSR and increased high frequency HRV) over the course of their visit (first several minutes compared to the last several minutes of the visit) will demonstrate greater improvements in GERD symptom severity than subjects who do not.

4. Healthcare providers in expanded visits will demonstrate more patient-centered non-verbal behaviors (e.g., smiles and gazes) and global impression (e.g., engaged, friendly, relaxed) compared to providers in standard visits as rated by blinded reviews of thin slices of video excerpts.
5. Patient and provider smiling at the end of study visits will be significantly associated with GERD symptom improvement 8 weeks later.

Primary outcome:

1. Change in the average daily GERD symptom severity score from baseline to the last week of the study in the expanded vs. standard group. GERD symptom severity is based on the sum of scores assessing the severity of daytime heartburn, nighttime heartburn, and acid reflux each on a 0-4 point scale (none, mild, moderate, severe, very severe; higher scores signify worse symptoms).

Secondary outcomes:

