9.2 Sample Size and Randomization

The combined standard deviation (root mean square error) in my pilot fellowship study was 1.5⁶⁴. We are conservatively assuming that this number will likely be larger in this study given the greater number of providers involved. Given 30 subjects in each group (n=60 total), 80% power, a two-sided significance test with alpha = 0.05, the minimal detectable difference (MDD) in GERD symptom severity scores between the standard and expanded groups given the estimated standard deviations (SD) is shown in the adjacent table. These MDD values are similar to those found in my fellowship study⁶⁴ and are clinically meaningful^{86,87}.

Minimal Detectable Difference Between Groups	
SD	MDD
1.5	1.10
2.0	1.47
2.5	1.84

Treatment Assignment Procedures

A randomization scheme will be devised before the start of the study by the study biostatistician who will retain the code and will be responsible for breaking the blind at the end of the study. We do not anticipate a need to break the blind during the study because we are not expecting serious adverse events to occur more frequently in one visit group than another. Randomization will be stratified by provider, with permuted block sizes of 2 and 4 with a goal to have 5-6 providers each see 10-12 subjects. If a provider cannot commit to this many visits, the study biostatistician may need to adjust the randomization scheme and we will consent additional providers.

The study biostatistician will enter the randomization scheme into REDCap and subjects will be randomized immediately prior to the study visit intervention.

If a subject drops out or is unable to complete the study, the statistician may need to rebalance the randomization scheme.

Subjects will be informed of their visit group assignment during the debriefing at the end of the second study visit.

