9.5.2 Secondary Outcomes

1. To analyze physiologic synchrony in GSR, first, an average slope of the GSR will be calculated in the patient and provider recordings in moving 5 second windows, offset by 1 second. Next, Pearson correlations with lag zero will be calculated over successive 15 second windows between time-locked patient and provider GSR slope values. Then, a single session index will be calculated from the ratio of the sum of the positive correlations across the entire visit divided by the sum of the absolute value of the negative correlations across the entire visit. To reduce skew, the natural logarithm of the index will be calculated. Thus, an index value of zero reflects equal positive and negative correlations, a value greater than zero reflects more concordance in GSR than not, while a value less than zero reflects less concordance in the dyad (less than 50%)⁸². These index values will be used in GLM analyses with GERD symptom severity and/or correlated with visit type.

We will also perform similar analyses on the HRV data – comparing variation in the beat-to-beat intervals over short segments of time and calculating Pearson correlation coefficients for time-locked patient and provider data for these intervals.

2. We will calculate absolute changes in both GSR and also high frequency HRV within study subjects from the beginning to the end of the study visit. We will assess the Pearson correlation between these changes and reported changes in GERD symptom severity. We will also look at absolute levels of GSR and HRV at the end of the study visit and compare those values with changes in GERD symptom severity in GLM models. As an exploratory analysis, I will test whether changes in GSR and HRV are a function of baseline perceived stress and if that relationship differs between the standard and expanded visit interventions.
3. To analyze study visit videos, 2 minute thin slices of each video at three time points (beginning, middle, and end of study visits) will be analyzed by trained and blinded coders, for the presence of 1) micro-level non-verbal supportive behaviors (e.g., gazes, smiles, nods, gestures – measured as absolute number or

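### Visits may be in person or by video link, yet no planned model contains visit mode, so the marker–symptom associations can be confounded

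*Combined protocol and SAP*

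**What the plan says.** Section 6.2.3, under physiologic measures and video recording, states that during the COVID-19 pandemic "the patient and doctor will sit in separate but adjacent, exam rooms with the door closed and use a video telehealth platform". The purpose is to record both faces unmasked. The arrangement is tied to the pandemic. No dates, switching rule or expected share of video visits are given.

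Other sections read as in-person. Section 4.3 has the provider learn the assigned visit type "immediately before walking into the room to conduct the study visit". Section 5.1 lists in the standard script "past medical history as well as a brief physical exam", and the expanded script builds on the standard one. Section 3 plans 2 years of enrolment.

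On analysis:

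- Section 9.2 stratifies by provider, with blocks of 2 and 4.
- Section 9.3 puts every randomized subject who had a visit into one intent-to-treat set.
- Section 9.5.1 specifies an ANCOVA with baseline severity and visit type, plus a list of exploratory moderators.
- Section 9.5.2 relates a GSR synchrony index, and a similar HRV analysis, to symptoms and visit type. It correlates within-visit GSR/HRV change with symptom change, and compares end-of-visit levels with symptom change.
- The same section has coders score behaviors such as "gazes, smiles, nods, gestures". These enter a model with time, visit type and their interaction, and each is then correlated with improvement.

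Visit type always means standard or expanded. Visit mode, in person or video, is in none of these places.

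**The concern.** The secondary outcomes measure the interaction itself: gaze, gestures, and moment-to-moment concordance of two people's autonomic signals. Whether the two share a room or see each other on a screen could plausibly affect all of these. Mode would also follow the calendar, since the pandemic drives it.

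Randomization protects the comparison of visit types. It does not protect the analyses that relate a marker to later improvement (secondary hypotheses 2, 3 and 5 in Section 9.1), because nobody is randomized to a level of synchrony or smiling. If mode shifts both the marker and improvement, an unadjusted Pearson correlation picks up mode and reports it as mechanism. Mechanism is what the secondary aims are about.

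Separately, Sections 5.1 and 6.2.3 do not fit together: no section says how the scripted examination is done when the provider is behind a closed door.

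**Working it through.** **1. The plan's own figure.** Section 9.2 gives 30 subjects per group, "80% power, a two-sided significance test with alpha = 0.05", and SDs of 1.5, 2.0 and 2.5. By normal approximation, MDD = SD × (1.960 + 0.842) × √(2/30), which at SD 1.5 is 1.5 × 2.802 × 0.2582 = 1.085. The noncentral t with 58 df gives 1.103, 1.471 and 1.839, against the stated 1.10, 1.47 and 1.84. The table reproduces.

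**2. Is mode balanced between arms?** Simulation, 4,000 runs per setting: 5 providers × 12 subjects or 6 × 10, blocks of 2 and 4 within provider, a calendar switch within each provider, and about 25%, 50% or 75% video. The arm difference in video share averages 0, with SD 6 to 9 percentage points and a 95th percentile of the absolute difference of 13 to 17 points. There is no systematic bias. For scale, a 17-point chance imbalance with a mode effect of 0.5 SD (0.5 × 1.5 = 0.75 points) moves the arm difference by 0.17 × 0.75 = 0.13 points, against an MDD of 1.10.

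**3. Precision of the primary comparison.** With video share p and a mode shift of g SD in symptoms, the SD is inflated by √(1 + p(1−p)g²). At p = 0.5 and SD 1.5:

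| g | SD inflation | Power at 1.10 | MDD |
|---|---|---|---|
| 0 | none | 79.8% | 1.10 |
| 0.25 | 0.8% | 79.1% | 1.11 |
| 0.5 | 3.1% | 77.3% | 1.14 |
| 1.0 | 11.8% | 70.5% | 1.23 |

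**4. Marker–symptom associations.** Suppose there is no true link, but mode shifts the marker by gx SD and improvement by gy SD in the same direction. With v = p(1−p),

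r = v·gx·gy / √[(1 + v·gx²)(1 + v·gy²)].

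The false-positive rate at n = 60 follows from Fisher's z, with mean atanh(r) × √57 and two-sided limits of ±1.96. For gx = 1, gy = 0.5, p = 0.5: r = 0.125 / √(1.25 × 1.0625) = 0.108; 0.109 × 7.55 = 0.82; the two tails sum to 0.130.

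| gx | gy | r (50% video) | False positives |
|---|---|---|---|
| 0.5 | 0.25 | 0.03 | 5.6% |
| 0.5 | 0.5 | 0.06 | 7.3% |
| 1.0 | 0.25 | 0.055 | 7.0% |
| 1.0 | 0.5 | 0.11 | 13.0% |

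At 25% video the same shifts give r of 0.02 to 0.08 and 5.3% to 9.8% false positives. In a separate simulation of 40,000 runs at 50% video, adjusting for mode brought the rate back to about 5%.

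**5. Cost of a mode term in the primary ANCOVA.** Going from 57 to 56 residual df moves the MDD from 1.1038 to 1.1041 at SD 1.5, taking that SD as residual and mode as balanced. A test of whether the visit effect differs by mode is another matter. At SD 1.5 it needs a difference of about 2.21 (50% video) or 2.55 (25% or 75% video) for 80% power, and has only 23% to 29% power for a difference of 1.10.

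**The case against.** **Both modes are not stated to occur.** A reader might infer that video and in-person visits are definitely pooled. The documents do not say so. The video link is conditional on the pandemic, and if every visit used one mode nothing would be pooled. This stands, and the fix is conditional for that reason.

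**No mode effect is documented.** No section says that mode changes gaze, GSR, HRV or symptoms. The shifts in the working are assumptions. This stands too.

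**Level shifts often cancel.** The GSR index is built from slopes and within-visit correlations, and patient GSR/HRV is also analysed as change over the visit. A constant offset between modes drops out of both, and out of the time and time-by-visit-type contrasts in the video model. For these, mode would have to alter concordance or trajectory. The cancellation does not reach the end-of-visit GSR/HRV levels or the behavior scores correlated with improvement.

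**A larger false-positive rate is tempting.** Shifts of 1 SD in both marker and improvement give r = 0.25/1.25 = 0.20 and about 34% false positives. But 1 SD in symptoms is 1.5 points at the pilot SD, more than the 1.10 the trial is sized to detect for its own intervention. Nothing in the protocol supports a mode effect that large.

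**Mode is largely recoverable, and the examination conflict is modest.** Visits are recorded and the recordings reviewed, so mode could be reconstructed afterwards. Entering the room could also mean the adjacent room. The visit scripts (Appendix E) are not reproduced in the text and may cover the examination. This lowers the stakes, but later reconstruction would not make the adjustment prespecified, and Sections 5.1 and 6.2.3 as written still disagree.

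**Conclusion.** The point holds as a limited one. Visit mode is missing from every specified stratum, covariate list and model, although the protocol provides for video visits and elsewhere describes in-person ones.

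A reader might conclude that the primary result is biased. It is not: mode does not depend on arm, allocation is blocked within provider, and the expected arm difference in video share is 0. For a symptom shift of 0.25 to 0.5 SD, power falls by only 0.7 to 2.5 percentage points.

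The exposure lies in the non-randomized marker–symptom analyses. At 50% video, with a marker shift of 0.5 to 1 SD and a symptom shift of 0.25 to 0.5 SD, a null marker shows r of about 0.03 to 0.11 and is declared significant about 6% to 13% of the time. These figures depend on assumed shifts and an assumed video share. With one mode only, or no mode effect on improvement, the inflation disappears. The conflict over the examination needs resolving in either case.

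**What to change.** - Record mode for each visit in REDCap and report it by arm.
- If both modes occur, add mode as a covariate in the GSR, HRV, video-coding and marker–symptom models, replacing raw Pearson correlations with partial ones. Write this into Section 9.5.2 before the data are examined, since that section already allows further models prompted by initial video results.
- Run the primary ANCOVA with mode as a sensitivity analysis. Any look at the visit effect by mode should be descriptive.
- Reconcile Sections 5.1 and 6.2.3 on the physical examination, so that both arms are handled alike within each mode.

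The cost is one data field, some wording, and one degree of freedom per model, about 0.0003 in the primary MDD at SD 1.5. Adjusting for mode does not by itself remove other calendar-time differences, such as a changing mix of providers or study medication. A separate gaze analysis within each mode is optional, as it would split 60 subjects.

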6.2.4 Blinding

This is a single-blinded study. Subjects will be unaware of the possibility for two different types of study visits. Study providers and staff will be aware of the study intervention delivered, but only immediately prior to the study visit to decrease the potential for introducing bias in how study staff interact with subjects during recruitment and consent. Subjects will be debriefed at the end of the Visit 2 regarding the nature of the study and the intervention that they

received. Data will be analyzed in a blinded fashion, also to avoid introducing bias. Given the low-risk nature of the study, we do not anticipate a need to break the blind while a subject is enrolled.

6.2.5 Post-Intervention Measures (Day 0)

Immediately following the study physician visit, subjects will be asked to complete the following questionnaires:

- Impressions of the Study Physician questionnaire – a 4 item measure assessing the patient’s impression of the study physician including overall rating of the physician, satisfaction with the physician, willingness to recommend the physician to others, and desire to see the physician again.
- Consultation and Relational Empathy questionnaire (CARE) – a validated and commonly used 10 item measure for assessing the quality of the patient encounter and perceptions of empathy from the treatment provider⁸⁰. I used it in my pilot study.
- HEAL Patient-Provider Connection – a subset of the Healing Encounters and Attitudes, a recently validated 7-item measure of the patient-provider connection. This is a patient-reported outcome developed as part of a set of tools to measure non-specific factors in treatment using the NIH PROMIS methodology⁸¹.
- Current Stress Question – 1 item self-report measure of current stress level on a scale of 0 (no stress) to 10 (extreme stress)

